Each group of students will go to classroom they were assigned at random. In the two classrooms, the same activities will be carried out for a duration of 2 hours, in which the students will have to remain in the classroom.

The chronology of the activities will be the following:

- Assignment of groups to classrooms and initial explanation of the activities (10 minutes).
- Completing the baseline Attention Network Task (ANT, adult version, Flanker task) (15 minutes).
- Completing the PMA-R (Primary Mental Aptitudes) test (10 minutes).
- Watch several videos related to Science and Environment (50 minutes).
- Completing a questionnaire about the videos (5 minutes).
- Completing the post Attention Network Task (10 minutes).
- Completing a questionnaire on factors that can affect attention, designed by the students (10 minutes).
- Completing a short version of the Global Preferences Survey (10 minutes).

The tests and questionnaires will be completed wearing headphones to block the noise.

Description of questionnaires and tests

Attention outcomes are all derived from the Attention Network Task-Flanker Task (ANT). It is a computerized test that takes approximately 9 minutes to complete. A row of five arrows appears either above or below a fixation point. Participants have to use the arrow keys from the keyboard to indicate as quickly as possible if the central arrow is pointing to the left or to the right. They have to ignore the flanker arrows, which point in either the same (congruent) or opposite (incongruent) direction than the middle arrow. The target can be preceded by no cue; a center cue or a double cue, which inform about the upcoming of the target but not on its location; or an orienting cue that alerts about the upcoming of the target as well as its location (orienting cue). The task includes four experimental blocks of 32 trials each (a total of 128 trials) (Forns et al. 2014).

A measure of intelligence is obtained from the PMA-R (Primary Mental Aptitudes - Reasoning) test. This test presents different series of letters, and the user has to guess which should be the next letter of the series by choosing one of the 6 options shown in the screen. The test lasts 6 minutes and the final score is the total number of correct responses.

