This is an interventional, randomized, 2-arm trial with equal allocation. Allocation will be done completely at random. Briefly, for each class in each high school, participating students will be randomly split into two equal-sized groups, and each group will go to a different classroom to perform the same activity for two hours. The two classrooms need to be as similar as possible in terms of size, orientation and windows. The two classrooms will have an identical air purifier (Pure Airbox, Zonair 3D) that will be running from 30 minutes before the session until the end of the 2-hour session. The purifier in one room will have the filters installed, and therefore will clean the air, while the purifier in the other classroom will not have the filters installed (sham device that will simply recirculate the air without filtering it). Participants will be masked to the intervention. Assignment of purifier to classroom will be done at random.

During the whole time, we will have measure continuously in both classrooms the concentrations of black carbon with Microaeth (AethLabs, USA), the concentration of PM_{2.5} with DustTrak (TSI, USA), the levels of CO₂ and values of temperature and humidity (Extech, USA).

Once students are in the classroom they have been assigned to, they will complete several activities, including several validated tests and tasks. All of them will be administered though a

laptop (each student will be provided one laptop with the tests and questionnaires). The tests and questionnaires will be completed using headphones to block the noise.

The chronology of the activities will be the following:

- Assignment of groups to classrooms, initial explanation (10 minutes).
- Completing the baseline Attention Network Task (ANT, adult version, Flanker task) (15 minutes).
- Completing the PMA-R (Primary Mental Aptitudes) test (10 minutes).
- Watch several videos related to Science and Environment (50 minutes).
- Completing a questionnaire about the videos (5 minutes).
- Completing the post Attention Network Task (10 minutes).
- Completing a questionnaire on factors that can affect attention, designed by the students (10 minutes).
- Completing a short version of the Global Preferences Survey (10 minutes).

Sample size Calculation

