A previous study (Sunyer et al., 2017) detected a mean reduction of 5 ms in the hit reaction time standard error for correct answers (HRT-SE) calculated from the ANT test, which we will take as our main outcome, associated with a 37% increase in the concentration of NO₂, a marker of exposure to traffic pollution. With the air purifier it is expected to achieve a 80% reduction in the concentration of fine particles, which is why we expect to find a difference of 10 ms in HRT-SE between the group that goes to the purified classroom and the ones that go to the regular classroom. Bearing in mind that the standard deviation of HRT-SE is 90 ms (Sunyer et al., 2017), to have a statistical power of 80% with a type I error of 5% in the comparison of the two groups, it is necessary to include 2,500 students. Assuming a participation of 25 of the 30 children for each participating class, the participation of 100 classes is required. By recruiting high schools with 2 or more lines, it is expected to have to recruit about 35 high schools.

Statistical analyses will be conducted after all information for all participants has been collected.

Statistical Principles

Statistical significance will be considered at the 5% level. Results will be provided with 95% confidence intervals.

Adherence to protocol will be defined as staying in the classroom during the 2 hours, or in exceptional cases, leaving it for less than 5 minutes. Adherence will be described as percentage of students being adherent. Non-adherent students will be excluded from statistical analyses.

Trial Population

Eligibility criteria: all students in the 3rd grade of ESO in participating high schools and with informed consent signed by them and by the parents will be eligible for the analysis. There are no exclusion criteria.

The CONSORT flow diagram will include the number eligible, the number that did not participate, the number allocated in each arm, the number not adherent (with reasons), and the excluded from the analyses (with reasons). Anticipated reasons for exclusion from analyses

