- Alerting score, computed subtracting the median reaction time (RT) in milliseconds for double cue from median RT for the no cue condition (calculations performed after removing the incongruent trials).
- Orienting score, computed subtracting the median RT in milliseconds for spatial cue from the RT for central cue (calculations performed after removing the incongruent trials).
- Conflict score (executive attention), calculated as the median RT in milliseconds for each flanker condition (across cue conditions) and subtracting the congruent from the incongruent RTs.

Analysis Methods

Analyses will be conducted using conditional linear regression using class (the group of 30 students from the same class in the same high school that were randomly split into each arm and that undertook the experiment on the same day and time) as strata. This way, the analysis will be automatically matched by high school, class, day and time of the day. Intervention arm will be the explanatory variable of interest in the model. The coefficient associated with arm will then be interpreted as the mean difference in the outcome when comparing the two arms. Models will be adjusted for year of birth; sex; average temperature during the experimental session; average relative humidity during the experimental session; and average CO₂ concentration during the experimental session; as these conditions can differ in the two classrooms.

Analysis of residuals will be used to detect influential observations using DFBeta. Analyses will be repeated by excluding subjects with DFBetas clearly separated from the rest.

Sensitivity analyses will include:

- Additionally adjusting the models for the same outcome measured in the baseline session.
- Additionally adjusting the models for the results of the PMA-R test (number of correct responses).

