- Replacing the arm indicator by the average values of black carbon from the beginning of the experiment to the end of the post ANT test. In this case, the effect of black carbon on the outcome will be reported by an interquartile range increase. This analysis will allow taking into account the difference in black carbon levels in the two classrooms, i.e. it will not estimate a common change in the outcome for all strata. Linearity of the association will be examined using generalized additive models (GAM). If visual inspection of the resulting exposure-response relationship suggests a non-linear association, we will try to transform variables to achieve linearity. If transforming variables does not work, we will report the curve estimated by the GAM models.
- Same as the previous point, but using PM_{2.5} levels instead of black carbon.

Subgroup analyses will be conducted by sex using the same methodology described above.

Missing Data

Missing data are only expected in the outcome variables if the participant did not complete the test, in which case it will be excluded. Other potential cases of missing data include an error in the monitors that precludes proper adjustment for covariates. If there are missing values for CO₂, temperature or humidity in one of the classrooms, we will replace them by the values from the other classroom, provided that this approach is reasonable according to the data obtained in the other classrooms. Otherwise, the classroom will be excluded from the adjusted analyses, but an unadjusted analysis including all classrooms will also be carried out to compare the results. For the analyses using black carbon or PM_{2.5} concentrations, missing values on these two variables will be imputed using the baseline value in the other classroom and the rate of reduction over time estimated in all other classrooms with sham or real air purifier, as appropriate.

Statistical Software

Analyses will be conducted in the Stata and R softwares. Stata command `xtreg` with the fixed effects option will be used to fit conditional linear regression models, which can also be fitted using regular linear regression commands in Stata (`regress`) or R (`lm`) by including a strata factor as adjustment variable. GAM models will be fitted using the `mgcv` package in the R software. The `tlm` package in R will be used to interpret models with transformed variables (Barrera-Gómez and Basagaña 2015).

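### Arm varies only between the two rooms of a class, but neither the standard error nor the sample size allows for residual correlation within a room

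*SAP*

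**What the plan says.** - **Design** (SAP, Trial Design and Randomization). Within each class "participating students will be randomly split into two equal-sized groups, and each group will go to a different classroom". One room has a purifier with filters and the other a sham device: "Assignment of purifier to classroom will be done at random".
- **Session** (Protocol, Participation of students in the classrooms). Activities last two hours, "in which the students will have to remain in the classroom".
- **Safeguards** (SAP, Trial Design and Randomization). The two rooms should be alike in size, orientation and windows, and "The tests and questionnaires will be completed using headphones to block the noise".
- **Model** (SAP, Analysis on Attention, Analysis Methods). "Analyses will be conducted using conditional linear regression using class" as strata, adjusted for year of birth, sex and the session averages of temperature, humidity and CO₂, "as these conditions can differ in the two classrooms".
- **Software** (SAP, Statistical Software). `xtreg` "with the fixed effects option will be used to fit conditional linear regression models", with `regress` or `lm` plus a class factor named as equivalents. No clustered or robust standard error, room random effect or analysis of room means is mentioned.
- **Sample size** (SAP, Sample size Calculation). A 10 ms difference with SD 90 ms, "to have a statistical power of 80% with a type I error of 5% in the comparison of the two groups", leads to 2,500 students, that is 100 classes of 25. No intraclass correlation or design effect appears.
- **Preference outcomes** (SAP, Analysis on Decision-making). These reuse the attention strategy alongside the method of a cited survey study.

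**The concern.** The comparison rests on about 200 room-sessions of 12 or 13 students, paired within 100 classes. Two sources of similarity within a room are already handled. Class strata remove school, class, day and time, and the random split means that room composition differs only by chance, which individual-level standard errors cover.

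What remains is anything that happens to one room after allocation, such as a disruption, the way the session is supervised or explained, or the lighting. The schedule puts 10+15+10+50+5 = 90 minutes in the room before the post ANT. Within a class, such an effect cannot be told apart from the filter effect; it only averages out across classes.

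A fixed-effects regression with default standard errors treats the students of a room as independent given class. If they are not, the confidence intervals are too narrow and the p-values too small for the primary attention outcome. The target difference is only 10/90 = 0.11 SD, so small room effects matter.

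**Working it through.** **1. The plan's own figure.** Inputs from the sample-size section: difference 10 ms, SD 90 ms, 5% (two-sided inferred, because one-sided gives 2,004), 80% power, 1:1 allocation.

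N = 4(1.96 + 0.8416)² × 90² / 10² = 2,543 (2,544 with arms rounded up). At 2,500 the standard error is √(4 × 8,100 / 2,500) = 3.6 ms, so power is Φ(10/3.6 − 1.96) = 79.3%. The plan's 2,500 is therefore the independent-students formula, and 2,500/25 = 100 classes with nothing added.

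**2. Variance with room correlation.** Let K = 100 classes, m = 12.5 students per room, ρ = share of the 90 ms variance lying between rooms within a class, and c = share lying between classes. Neither ρ nor c is in the documents; both ranges are assumptions.

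V = [2ρ + 2(1 − c − ρ)/m] × 8,100 / K

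Relative to the plain formula, the required N is multiplied by 1 + (m − 1)ρ − c.

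**3. Variance the default standard error reports.** This is 2s²/1,250, where s² is the residual mean square after class effects:

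s² = [2K(m − 1)σe² + (K − 1)(mσr² + σe²)] / (2Km − K − 1)

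Example with ρ = 0.01, c = 0, so σr² = 81 and σe² = 8,019:
- V = (0.02 + 0.1584) × 81 = 14.45
- s² = [2,300 × 8,019 + 99 × 9,031.5] / 2,399 = 8,061, so the default variance is 12.90
- ratio R = 14.45/12.90 = 1.120
- default standard error too small by 1 − 1/√1.120 = 5.5%
- type I error = 2[1 − Φ(1.96/√R)] = 6.4%
- power with a valid standard error = Φ(10/√14.45 − 1.96) = 74.9%

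**4. Results over the assumed range** (type I error at c = 0):

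| ρ | Room SD (ms) | R | Default SE too small by | Type I error | Power, c = 0 | Power, c = 0.10 |
|---|---|---|---|---|---|---|
| 0 | 0 | 1.000 | 0% | 5.0% | 79.3% | 83% |
| 0.005 | 6 | 1.060 | 3% | 5.7% | 77.1% | 81% |
| 0.01 | 9 | 1.120 | 5.5% | 6.4% | 74.9% | 79% |
| 0.02 | 13 | 1.242 | 10% | 7.9% | 70.7% | 74% |
| 0.05 | 20 | 1.614 | 21% | 12.3% | 60.0% | 63% |

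The power columns use the normal distribution; a t reference on 99 df takes off about 1 point. At c = 0, 80% power would need 2,690, 2,837, 3,129 and 4,007 students at ρ = 0.005, 0.01, 0.02 and 0.05.

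**5. What class matching does.** With c = 0.10, power stays at or above 80% up to ρ of about 0.007: 2,543 × (0.90 + 11.5ρ) = 2,500 gives ρ = 0.0072. Type I error is not repaired: with c = 0.10 it is 6.6% at ρ = 0.01 and 8.2% at ρ = 0.02.

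**6. Simulation of type I error** (100 classes, rooms of 12 and 13, class fixed effects), at ρ = 0, 0.01, 0.02, 0.05:
- With three room-level covariates plus sex, 10,000 replicates: default 5.1%, 6.5%, 8.0%, 12.4%; class-clustered 5.5%, 5.4%, 5.4%, 5.6%.
- Without covariates, 20,000 replicates: default 4.8%, 6.1%, 8.2%, 12.2%; class-clustered 4.7% to 5.2%.
- A further run with three room-level covariates: default 5.0%, 5.5%, 7.3%, 11.4%; class-clustered 4.5% to 5.2%.

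With the room-level covariates and c = 0, simulated power with clustered errors was 77.4%, 72.5%, 69.1% and 58.5% (3,000 replicates), so that adjustment costs a further 1 to 2 points.

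**The case against.** **The room correlation is assumed.** This is true. At ρ = 0 the plan is sound. Even ρ = 0.01 means a nuisance room SD of 9 ms, close to the 10 ms expected from the purifier, left over after similar rooms, headphones, and temperature, humidity and CO₂ adjustment. At ρ = 0.05 the room SD is twice the expected effect; that row is the far end of an assumed range, not a likely value. But nothing in the plan shows that the remainder is zero, and the headphones are specified for the tests and questionnaires, not for the whole session.

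**Baseline ANT adjustment would absorb lasting room effects.** In part it would, because the baseline test is taken in the assigned room. If the baseline-to-post correlation were 0.5 and room effects fully persistent (both assumptions), about (1 − 0.5)/(1 + 0.5) = one third of ρ would remain. In the SAP, however, this is only a sensitivity analysis, and it does not touch effects that arise later in the session.

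**Clustering gains little at very small ρ.** This also stands. In one simulation clustered errors ran at 5.4% to 5.6%, hardly different from the default's 5.7% at ρ = 0.005. The gain grows with ρ: at 0.02 the default gives 7.3% to 8.2% across the simulations.

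**The power deficit is not demonstrated.** Correct: its sign depends on ρ and on how much of the 90 ms is between classes. The class share must be at least 11.5 times the room share to offset the loss.

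**Class may be the wrong cluster level.** The documents do not say whether classes in a school reuse the same two rooms with the same purifier placement. If they do, room effects could be shared across classes. This bears on the level of clustering, not on the need for it.

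**Default errors are inferred from silence.** They are. The text before the SAP's background summary was not available, but the analysis and software sections, where an estimator belongs, were, and they name none.

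**Conclusion.** The concern holds as stated: 5% type I error and 80% power are not assured. The documents do not show that either is actually wrong. The structural facts are plain in the text: arm coincides with room within class, no variance estimator allows for room correlation, and 2,500 is an independent-students figure.

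The size depends on ρ, which the documents do not give. For ρ from 0.01 to 0.02, an assumption, type I error is about 6.4% to 7.9% and power about 75% to 71%, or 79% to 74% if a tenth of the variance lies between classes. At ρ = 0 nothing is lost beyond 79.3% for 80%.

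This should be fixed before analysis because the remedy is nearly free. For the preference outcomes the point applies only so far as they follow the attention strategy. How the cited source computes its standard errors cannot be seen from the documents, and no calculation was made for those outcomes.

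**What to change.** - **SAP, Analysis Methods and Statistical Software.** Keep the class fixed effects and state that standard errors are clustered on class, for example `xtreg ..., fe vce(cluster class)`, with a t reference of about 99 df, or somewhat fewer after the three room-level covariates. A paired analysis of within-class differences in room means, filtered minus sham, is acceptable but is not the identical estimator. Room cannot be added as a fixed effect, because within a class it is collinear with arm.
- **Room use.** State whether classes in a school share the same two rooms and whether the purifier is re-randomised for each class. If rooms and placement are reused together, cluster on school (about 35).
- **Scope.** Apply this to all attention outcomes and to the preference regressions that follow the same strategy.
- **Sample size, SAP and protocol.** Restate power for 2,500 students in 200 rooms over an explicit range of residual room correlation, and state the class share assumed within the 90 ms SD.

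**Cost.** One command option and a few sentences; no new data. Intervals may be slightly wider and the stated power somewhat lower. If room correlation is zero almost nothing is lost: simulated power was 77.4% with class-clustered errors and 77.7% with default errors.

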Previous observational studies have reported an association between higher air pollution exposure and lower attention in children. With this project, the investigators aim to confirm this association in adolescents using an experimental design. In addition, the study will assess the relationship between air pollution exposure and individual decision-making with respect to risk, time and social considerations. High school students in 3rd grade (ESO, 14-15 years of age) in different high schools in the Barcelona province (Spain) will be invited to participate. For each class in each high school, participating students will be randomly split into two equal-sized groups. Each group will be assigned to a different classroom where each participant will complete several activities during two hours, including an attention test (Flanker task) and a reduced version of the Global Preferences Survey. One of the classrooms will have an air purifier that will clean the air. The other classroom will have the same device but without the filters, so it will only re-circulate the air without cleaning it. Students will be masked to intervention allocation. The investigators hypothesize that students assigned to the clean air classroom will have better scores in the attention test, and that decision-making will also present differences between the two classrooms.

Objectives

The objectives of the study are to identify if cleaning the air of a classroom has an impact on:

- 1) The attention of high-school students
- 2) The individual preferences with respect to risk, time and social considerations

Study Methods

Trial Design and Randomization

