include: missing data in an outcome (the subject will be excluded from the analyses of that outcome) or low accuracy tests. For ANT, a test will be considered of low accuracy if the number of correct responses is less than 70%. Reaction times (RT) below 100 ms will be excluded from RT calculations because of physiological implausibility implying that such a response is perseverative or anticipatory, although this does not imply the exclusion of the subject (other RT are available).

Baseline characteristics will be summarized by providing, for each arm, percentages for categorical variables and medians and 1st and 3rd quartiles for continuous variables. The following baseline variables will be summarized: sex, age, PMA-R results, and baseline ANT measures.

Analysis

Analysis on Attention

Outcomes

Attention outcomes are all derived from the Attention Network Task-Flanker Task (ANT). It is a computerized test that takes approximately 9 minutes to complete. A row of five arrows appears either above or below a fixation point. Participants have to use the arrow keys from the keyboard to indicate as quickly as possible if the central arrow is pointing to the left or to the right. They have to ignore the flanker arrows, which point in either the same (congruent) or opposite (incongruent) direction than the middle arrow. The target can be preceded by no cue; a center cue or a double cue, which inform about the upcoming of the target but not on its location; or an orienting cue that alerts about the upcoming of the target as well as its location (orienting cue). The task is divided into four experimental blocks of 32 trials each (a total of 128 trials).

The primary outcome regarding attention will be the response speed consistency throughout the post Attention Network Task-Flanker Task (ANT). It will be calculated as hit reaction time standard error (in milliseconds) for correct responses (HRT-SE). A higher HRT-SE indicates highly variable reactions related to inattentiveness.

Secondary outcomes include the following, derived from the post ANT:

- Impulsivity, calculated as the number of incorrect responses (responses made in the opposite direction to the direction of the target arrow).
- Selective attention, calculated as the number of omission errors (failure to respond to the stimulus).

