Analysis on Decision-making with respect to Risk, Time and Social Considerations

Outcomes

The primary outcomes of analysis will be the (1) risk taking scores, (2) time preference scores, (3) the positive reciprocity scores, (4) the altruism scores, and (5) the self-assessment of trust. All the scores will be measured from the responses to the questionnaire, which is a subset of the questionnaire in Spanish used in Falk et al (2018). For each of the traits (risk preferences, time preferences, positive reciprocity, altruism, and trust), an individual-level index will be computed that aggregates responses across different survey items following the methodology in Falk et al. (2018).

Analysis Methods

The analysis will follow the basic analysis of Falk et al (2018), where groups, instead of being countries, will be our arms. In addition, we will follow the empirical strategy described above for the analysis on attention. That is, we will perform regression analysis, controlling for the relevant observable variables such as gender, age, cognitive ability, attention outcomes, and other physical variables measured at the time of the experiments such as temperature, relative humidity, or average CO₂ concentrations. We will also control for outliers, and will study heterogeneous treatment effects.

Missing Data

In terms of missing values in the questionnaire on preferences, we will follow the methodology of Falk et al (2018, Section I.H): “If one (or more) survey items for a given preference were missing, then the missing items will be predicted using the responses to the available items:

- Suppose the preference was measured using two items, call them *a* and *b*. For those observations with missing information on *a*, the procedure will be to predict its value based on the answer to *b* and its relationship to *a*, which was estimated by regressing *b* on *a* for the subsample of subjects who had nonmissing information on both, *a* and *b* (on the world sample).
- For the unfolding-brackets time and risk items, the imputation procedure will be similar, but making additional use of the informational content of the responses of participants who started but did not finish the sequence of the five questions. Again suppose that the preference is measured using two items and suppose that *a* (the staircase measure) is missing. If the respondent did not even start the staircase procedure, then imputation will be done

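### The preference regressions adjust for attention outcomes, most naturally those from the post test, so the arm coefficient is not the total effect of clean air that objective 2 asks for

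*SAP*

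**What the plan says.** The SAP's Objectives section introduces the aims with "The objectives of the study are to identify if cleaning the air of a classroom has an impact on", and the second item is individual preferences on risk, time and social considerations. The protocol (Outcome Measures) names six primary outcomes: one attention measure and five preference scores.

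For the preference scores, the SAP (Analysis on Decision-making, Analysis Methods) first refers to the analysis of the cited preference study, with arms in place of countries. It then adopts the strategy of the attention analysis, "controlling for the relevant observable variables such as gender, age, cognitive ability, attention outcomes" together with temperature, humidity and CO₂. The list of controls is open-ended, and the ANT session is not named.

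Elsewhere the SAP is specific about sessions. Under Analysis on Attention, Outcomes, the primary outcome is defined on the post ANT, and the others are introduced with "Secondary outcomes include the following, derived from the post ANT". The first session is labelled as baseline: "The following baseline variables will be summarized: sex, age, PMA-R results, and baseline ANT measures" (Trial Population).

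In the attention strategy that the preference analysis borrows, "The coefficient associated with arm will then be interpreted as the mean difference in the outcome when comparing the two arms". There, adjustment for the baseline-session ANT and for the reasoning test (PMA-R) appears only among the sensitivity analyses.

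**The concern.** Read naturally, the preference model conditions on a variable measured after randomisation that is itself a primary outcome and is expected to respond to the intervention. The protocol's Introduction derives the possible effect of pollution on preferences from cognitive function, citing evidence for time and risk only. On that reasoning attention is a candidate mediator, and holding it fixed removes whatever part of the effect passes through it.

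What remains need not be a clean direct effect either. If attention and preferences share unmeasured causes, such as tiredness or motivation on the day, conditioning on attention introduces an association between arm and those causes that randomisation had removed. The trial could then understate a real effect on preferences, overstate one, or show an arm difference where clean air does nothing to preferences. This concerns five of the six primary outcomes, and the SAP sets out no preference model without attention.

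**Working it through.** **Plan's own figures.** The listed activities sum to 10+15+10+50+5+10+10+10 = 120 minutes, matching the two-hour session. For the sample size, a two-sided 5% test, 80% power, a 10 ms difference and SD 90 ms give 1,272 per arm, or 2,544 in total. That is within 2% of the stated 2,500; power at 1,250 per arm is 79.3%.

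**Timing** (SAP, Trial Design and Randomization). The activities before the post ANT take 10+15+10+50+5 = 90 minutes. The post ANT therefore occupies minutes 90–100 and starts at 90/120 = 75% of the session. The preference survey follows the 10-minute student questionnaire and occupies minutes 110–120.

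**Inputs for size.**
- Arm effect on attention, scored so that higher is better: a = 10/90 = 0.111 SD (SAP, Sample size Calculation).
- N = 2,500 with equal arms: SE of an arm difference in SD units = √(4/2500) = 0.040.
- Detectable difference at 80% power = (1.960 + 0.842) × 0.040 = 0.112 SD.
- Within-arm slope b of preference on attention, in SD per SD: not in the documents. **Assumed** at 0.1, 0.2 and 0.3, either sign. At b = 0 there is no shift.

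**Formulas** (one attention measure).
- Adjusted minus unadjusted arm coefficient = −a × b.
- Adjusted SE = 0.040 × √[(1 − b²)(1 + a²/4)].

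| b | Shift (SD) | Adjusted SE | Power if true total effect is 0.112 SD | Rejection if no effect on preferences and b comes only from shared causes |
|---|---|---|---|---|
| +0.1 | −0.011 | 0.0399 | 72% | 5.9% |
| +0.2 | −0.022 | 0.0393 | 63% | 8.7% |
| +0.3 | −0.033 | 0.0382 | 54% | 14.1% |
| −0.1 | +0.011 | 0.0399 | 87% | 5.9% |
| −0.2 | +0.022 | 0.0393 | 93% | 8.7% |
| −0.3 | +0.033 | 0.0382 | 97% | 14.1% |

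Worked case, b = +0.3: 0.112 − 0.033 = 0.079 SD; 0.079/0.0382 = 2.06; power = Φ(2.06 − 1.96) = 54%. For b = −0.3 the coefficient is 0.145 SD.

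Relative to the detectable difference, the shift is 0.011/0.112 = 10% to 0.033/0.112 = 30%.

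**Simulation check.** The setting was 4,000 trials of 100 classes of 25, class fixed effects, a slope of 0.3 from a shared cause and no effect on preferences. The 5% test rejected in 5.1% of trials without the attention covariate and 13.8% with it, in line with 14.1% from the formula.

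**The case against.** The main counter-argument concerns the reading. In the preference model the attention term stands beside sex, age and cognitive ability, which are background characteristics. The attention strategy that the model borrows has two optional adjusters, the baseline-session ANT and PMA-R, and the phrase may mean that pair. One sensitivity-analysis bullet even applies the word outcome to the baseline session. This leaves the baseline reading possible but does not make it the natural one: that bullet names the baseline session explicitly, as the SAP does elsewhere, and the preference section does not. The ambiguity itself decides which effect is estimated.

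It can also be said that the control list is open and that the cited study's analysis may be a plain group comparison. Neither commits the SAP to a model without attention, because that analysis is not described. The unadjusted analysis mentioned under Missing Data is tied to missing monitor readings, so it is no safeguard.

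The size is open to fair challenge. The slope is assumed. For reciprocity, altruism and trust the documents cite no link with cognition, so a slope of zero is possible. PMA-R in the same model could absorb some shared-cause correlation. The 14% figure needs a residual slope of 0.3 arising wholly from shared causes plus the full 10 ms effect on attention, and is best read as the upper end of the range. Even there the shift (0.033 SD) is below one standard error. These points limit the magnitude; they do not restore the total effect as the quantity estimated.

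**Conclusion.** The concern holds. Taken as written, the preference model conditions on a post-randomisation primary outcome, and its arm coefficient is neither the effect in objective 2 nor the between-arm mean difference that the SAP says it represents. The documents do not fix the direction of the error. It is toward zero if the direct and attention-mediated effects share a sign and shared causes are weak; otherwise it can be away from zero.

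The size rests on the planned 0.111 SD effect on attention and an assumed slope: nothing at slope 0, and 0.011 to 0.033 SD at slopes of 0.1 to 0.3. If attention were the only path from clean air to preferences, adjustment would remove the whole effect.

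If the baseline ANT was intended, the problem is much smaller, though not nil: that test starts at minute 10 of the session, after 40 minutes of purifier running.

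**What to change.** Specify in the SAP that the main model for each of the five preference outcomes contains arm, class strata, sex, year of birth and the room covariates of the attention model (temperature, relative humidity, CO₂), with no post-ANT measure. Report any model that adds post-ANT attention only as a labelled exploratory mediation analysis. If the baseline ANT was meant, name it.

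Placing PMA-R and baseline ANT in sensitivity analyses would match the attention analysis. It is a matter of consistency and is not needed to remove the bias.

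The change is to SAP wording only; data collection and sample size are unaffected. The cost is the precision the covariate would have given: at an assumed slope of 0.3 the standard error rises from about 0.038 to 0.040 SD, or about 5%.
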